3. SYNOPSIS

The Trial will review the use of a mobile-based 6MWT by hospital outpatients during the coronavirus pandemic and evaluate its use

Trial Title	Evaluation of the usefulness of adopting remote, mobile-based 6MWT among hospital outpatients (the 6-APP now Study), within the constraints imposed by the SARS-COV2 pandemic.		
Internal ref. no. (or short title)	6-APPnow Study		
Trial registration	Clinical Trials. gov		
Sponsor	Oxford University Hospitals NHS Foundation Trust [name]		
Funder	NIHR BRC and the Swedish Knowledge Foundation		
Trial Design	Patient survey to evaluate their use of the 6 minute walk test smartphone app as a surrogate for regular clinic 6MWT.		
Trial Participants	Patients using 6 minute walk tests for managing cardiopulmonary function or disease management		
Sample Size	250-500 patients attending the outpatient clinics		
Planned Trial Period	Q2 2021 – Q2 2022		
Planned Recruitment period	Q2 2021 – Q2 2022		
	Objectives	Outcome Measures	Timepoint(s)
Primary	To assess whether patients are able and willing to use a smartphone app for the 6MWT	Percentage of participants who perform at least one app-based 6MWT before patient consultation.	At 3, 6, 9 and 12 months after the start of the study.
Secondary	
To assess the accuracy of the app-based measurement.
 
To assess whether differences in distance walked altered management of patients.
	
Measurement of walked distance (6MWD) measured by the app compared with a trundle wheel reference.
 
Number of clinical investigations and multidisciplinary team discussion triggered by variations in app-based 6MWD.
	
12 months
 
At 3, 6, 9 and 12 months after the start of the study.

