6. OBJECTIVES AND OUTCOME MEASURES

The population to be studied is composed of hospital outpatients who have conditions where the 6MWT is routinely used in clinical care, and/or are using the 6APP as an alternative.

The objective is: To evaluate the usefulness of adopting remote, mobile-based 6MWT among hospital outpatients, within the constraints imposed by the SARS-COV2 pandemic.

Objectives	Outcome Measures	Timepoint(s) of evaluation of this outcome measure (if applicable)
Primary Objective To assess whether patients are able and willing to use a smartphone app for the 6MWT	Percentage of participants who perform at least one app-based 6MWT before patient consultation.	At 3, 6, 9 and 12 months after the start of the study.
Secondary Objectives To assess the accuracy of the app-based measurement. To assess whether differences in distance walked according to the app altered management of patients.	Comparison of walked distance (6MWD) measured by the app versus a trundle wheel reference. Number of clinical investigations and multidisciplinary team discussion triggered by variations in app-based 6MWD.	12 months. At 3, 6, 9 and 12 months after the start of the study.

To assess the usability and acceptance of the app.	Standard usability and acceptance questionnaires, semi-structured interviews.	12 months.
To collect raw data from phones' sensors to allow the development of future algorithms for app-guided 6MWT.	Localisation position (GPS), speed, acceleration, step count, gyroscope samples collected during 6MWT.	12 months.
To determine whether the use of the 6MWT reduces time spent and number in hospital visits.	Time spent in hospital attendances and number of hospital visits made during use of the 6MWT compared with previous periods.	12 months.
To compare the use of 6MWT during pandemic with pre-pandemic use.	Total number of 6MWTS performed during 2020 pandemic period compared with pre-pandemic period.	12 months.

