9.2. Baseline Assessments

There is no baseline assessment of each patient, however, we will request baseline statistics about 6MWT performed during 5 years previous to the pandemic. These data will be pulled from the electronic health record. Only the patient ID and the date of the 6MWT are needed for this analysis.

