9.6. Definition of End of Trial

The study ends 12 months after the first patient has been recruited or when restrictions to clinical practice due to the pandemic are lifted.

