We will estimate the time spent in hospital attendances and the number of hospital visits made during the study period and compare it with previous 5 years.

Compare the use of 6MWT during pandemic with standard care.

We will compute statistics regarding the number of 6MWT available per patient over the last 5 years and compare them with the number of available 6MWT results within the study period. This will help identify the difference between the number of 6MWT per patient per year before the pandemic (standard 6MWT in clinic) and after the pandemic (using the app).

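### The two before/after secondary outcomes (hospital visits and 6MWT use) are defined over different periods in different sections, and an uncontrolled contrast is used to judge whether use reduces visits

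*Combined protocol and SAP*

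**What the plan says.** **6MWT use.** Section 6 (and Section 3 in the same terms) defines the outcome as "Total number of 6MWTS performed during 2020 pandemic period compared with pre-pandemic period". The planned trial and recruitment periods in Section 3 are both "Q2 2021 – Q2 2022". Section 9.2 (Baseline Assessments) sets the baseline: "we will request baseline statistics about 6MWT performed during 5 years previous to the pandemic". Section 12.1 takes 6MWT counts per patient "over the last 5 years and compare them with the number of available 6MWT results within the study period". Its next sentence gives the target as the difference between "the number of 6MWT per patient per year before the pandemic (standard 6MWT in clinic") "and after the pandemic (using the app").

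**Hospital visits.** Section 3 compares attendance time and visit numbers while the app is in use with earlier periods that it does not define. Section 6 does the same but refers to use of the 6MWT, not the app. Section 12.1 instead compares "the number of hospital visits made during the study period and compare it with previous 5 years". The objective asks whether use reduces visits and time spent.

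**Context.** Section 9.1 (Enrolment) says that patients are not randomised, and no comparator group is described. Section 5.3 says that telephone contact was already replacing face-to-face visits, and that the usual clinic regime for PAH patients had been abandoned. Under Section 9.6 the study runs 12 months from first recruitment or ends "when restrictions to clinical practice due to the pandemic are lifted", so the length of the study period is not fixed.

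**The concern.** Two analysts who follow different sections would compute different quantities under the same outcome name. For 6MWT use they would differ in calendar window and in unit. For visits they would differ in window and baseline, and neither would find a rate unit or a specified extraction. The periods could then be settled after the data are seen.

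The second issue is attribution. The visits objective is worded causally, and Section 17.2 says that the study aims to lower the number of patients needing clinic visits. A fall against earlier years would readily be reported as a benefit of the app, although the plan contains nothing that separates the app from the pandemic's own effect on attendance.

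**Working it through.** The documents give no sample size, power or visit rate for these outcomes, so there is no stated figure to reproduce. The check is a comparison of the definitions and some window arithmetic.

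**1. Definitions side by side**

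| | Sections 3 and 6 | Section 9.2, Baseline Assessments | Section 12.1 |
|---|---|---|---|
| 6MWT use: comparison period | 2020 pandemic period | – | study period |
| 6MWT use: baseline | pre-pandemic, length not given | five years before the pandemic | last five years, then a before-pandemic rate |
| 6MWT use: unit | total | – | per patient per year |
| Visits: comparison period | during use (app in 3, 6MWT in 6) | – | study period |
| Visits: baseline | earlier periods, undefined | – | previous five years |
| Visits: unit | none | – | none |

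**2. Overlap of the two comparison periods for 6MWT use.** The earliest planned start is 1 April 2021 and 2020 ends on 31 December. Shared months: 0.

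**3. Pandemic months in a literal five-year look-back from study start.** Section 5.3 says that the shielding arrangement lasted five months, until August, which puts onset in March or April 2020 (inferred; no date is given). Study start lies between 1 April and 30 June 2021.
- Shortest: 1 April 2020 to 1 April 2021, m = 12 months; 12/60 = 20%.
- Longest: 1 March 2020 to 30 June 2021, m = 16 months; 16/60 = 27%.
- A baseline ending at pandemic onset contains 0 such months.

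If testing in those months ran at a fraction g of normal (assumed), the study-to-baseline ratio for 6MWT use is inflated by 60/(60 − m + g·m):
- g = 0.75: 60/57 = 1.05 to 60/56 = 1.07
- g = 0.50: 60/54 = 1.11 to 60/52 = 1.15
- g = 0.25: 60/51 = 1.18 to 60/48 = 1.25

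This applies only if the look-back is taken literally.

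**4. What the visits contrast shows with no app effect.** Suppose that pandemic policy alone cuts the visit rate by a fraction f (assumed; the documents give no rates), and that rates are annualised correctly. The apparent fall is f against a pre-pandemic baseline, and 1 − (1 − f)/(1 − f·m/60) against the literal last five years.

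| f | Pre-pandemic baseline | Last five years, m = 12 | Last five years, m = 16 |
|---|---|---|---|
| 25% | 25% | 1 − 0.75/0.95 = 21% | 1 − 0.75/0.933 = 20% |
| 50% | 50% | 1 − 0.50/0.90 = 44% | 1 − 0.50/0.867 = 42% |
| 75% | 75% | 1 − 0.25/0.85 = 71% | 1 − 0.25/0.80 = 69% |

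In these scenarios the choice of baseline moves the result by at most about 8 percentage points (50 − 42). The pandemic's own effect accounts for all of the apparent fall under either baseline. Tidying the baseline therefore makes the outcome reproducible but does not make it attributable.

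**The case against.** Several defences stand, and they limit the point.

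- **6MWT use does have a time denominator.** Section 12.1 states it per patient per year. The fault there is disagreement with the total in Sections 3 and 6, not absence. The sentence that follows the five-year look-back, together with Section 9.2, points to a pre-pandemic baseline, so the look-back is probably loose wording for this outcome. Nothing similar settles the baseline for visits.
- **The phrase placing the study after the pandemic is not a separate error.** The Section 12.1 heading for this analysis speaks of use during the pandemic, so the phrase reads naturally as after onset.
- **Visit data are not confined to the study spreadsheet.** A reader might infer that the outcome cannot be computed, because the log does not code telephone and face-to-face consultations separately and the baseline query covers only patient ID and test date. But Section 12.1 does not say that the spreadsheet is the only source, Section 13.1 (Source Data) lists hospital records, and the restriction in Section 9.2 concerns the 6MWT baseline. What stands is that no section specifies the extraction of face-to-face visits or attendance time.
- **Large artefacts can be constructed but are not planned.** Raw counts over 12 against 60 months would show an 80% fall at a constant rate (1 − 12/60), or 90% with even enrolment over 12 months and counting from enrolment (1 − 6/60). Counting from enrolment but dividing by 12 months would show a fall of 12.5% to 50% (1 − 10.5/12 to 1 − 6/12, for even enrolment over 3 to 12 months). Section 12.1 states none of these calculations and annualises the companion outcome. They are worst-case readings, not consequences of the plan.
- **Attribution could be handled as a limitation.** The analysis is descriptive and the absence of randomisation is open. That is fair, but the objective still asks a causal question that the design cannot answer.

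**Conclusion.** The concern holds for two secondary outcomes and should be fixed. The definitions of both outcomes conflict across Sections 3, 6 and 12.1. For 6MWT use the two comparison periods have no month in common. For visits there is also no rate unit, no dated baseline and no specified extraction, and a literal five-year look-back would contain about 12 to 16 pandemic months of 60 (20–27%). The uncontrolled contrast cannot show whether use reduces visits, because a fall could appear with no app effect.

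The 12 to 16 months rest on an onset inferred from Section 5.3 and a start within Q2 2021. The values of f and g are assumptions, and the true effect of the pandemic on visits is unknown from the documents. No hypothesis test or success criterion is planned, so the harm is to interpretation and to the freedom to choose periods afterwards, not to an error rate. The primary outcome is not affected.

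**What to change.** Align Sections 3, 6, 9.2 (Baseline Assessments) and 12.1 as follows.

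1. Use one baseline for both outcomes: the five years ending on a stated date before the pandemic.
2. Use the study period as the comparison window for both, replacing the reference to 2020. Report the months from pandemic onset to study start separately where available. They partly show the pandemic's own effect, with the limit that some patients were already using the app (Section 9.1, Recruitment).
3. Report both outcomes as rates per patient-year, with one stated start of follow-up. It should be consistent with Section 12.1, which counts app tests from confirmed download, and with the during-use wording in Section 3. The dated APP-OK log entry is a candidate.
4. Show clinic and app 6MWTs separately; the log in Section 9.3 (Subsequent Visits) already codes them separately.
5. Take face-to-face visits and attendance time from the hospital record in both periods, or drop time spent if the record does not hold it.
6. Reword the visits objective as a descriptive comparison, and state that it cannot separate the app from the pandemic.

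The cost is mainly wording, plus a record query wider than patient ID and test date (patient-year rates also need time under care), which may need approval as an amendment under Section 17.5. The visits result would no longer support a claim of app benefit.

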9.3. Subsequent Visits

Part 1: logging events

At each consultation, either through phone or face to face visit, the clinician who contacts the patient will log on the spreadsheet the distance walked and a series of study-related events, marked with a code. Coding is needed to simplify and automate later analysis. The following is an example of the structure of the spreadsheet:

Patient number	hospital	Date	Event	Comments

Events codes are explained in the following table:

Event	Code	Example comments
The patient accepts to join the study and provides consent.	RECRUIT-ACCEPT	Patient has accepted to join the study.
The patient denies consent and does not join the study.	RECRUIT-DENY	Patient denies consent because of lack of time.
The patient has decided to withdraw from the study.	RECRUIT-WITHDRAW	Patient's conditions have worsened and she cannot walk 6 minutes any more.
The patient declares to have the app installed on a phone he/she can use.	APP-OK	Patient has downloaded the app, everything works as expected.
The patient declares that he/she is having technical issues with the app.	APP-ISSUE	The app crashes when started on iPhone 11.
The patient shares a 6MWT not older than 2 weeks either through email or by telephone.	APP-6MWT	Date: 3/5/2021, distance: 420 m
The patient needs further evaluation because of changed medical conditions. The role of the app-based 6MWT is also coded depending on whether it was irrelevant to the decision, partially involved or fundamental for the decision. The event is logged once per decision (further contacts with the patient resulting from the decision should not include the tag).	NEW-EVAL-NO-6MWT NEW-EVAL-PART-6MWT NEW-EVAL-FULL-6MWT	The patient shows a general deterioration, last 6MWT was below 300m. An MDT is required.
The patient needs a change in the treatment. The role of the app-based 6MWT is specified as above.	NEW-TREAT-NO-6MWT NEW-TREAT-PART-6MWT NEW-TREAT-FULL-6MWT	Medication regime increased because of a lower 6MWD in the last 4 weeks.

Regular clinic 6MWT	CLINIC-6MWT	Date: 23/4/2021, distance: 450m
Additional observations	EXTRA-OBS	Because of reduced risk of corona infection, patient is invited to the clinic.

A list of possible codes with their explanation will be included in a tab of the spreadsheet.

Part 2: accuracy, usability and acceptance assessment

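### Section 12.1 does not say whether clinic, app or all 6MWTs count during the study, and clinic tests come from different sources in the two periods

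*Combined protocol and SAP*

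**What the plan says.** The last analysis in section 12.1 takes the "number of 6MWT available per patient over the last 5 years" and says the team will "compare them with the number of available 6MWT results within the study period". That sentence does not restrict the study-period side to one kind of test. The next sentence, on what the comparison will show, sets the yearly number per patient "before the pandemic (standard 6MWT in clinic) and after the pandemic (using the app". The objectives tables in the synopsis and section 6 define the outcome as a total of 6MWTs, again without a mode.

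On sources, section 9.2 (Baseline Assessments) states "we will request baseline statistics about 6MWT performed during 5 years previous to the pandemic", and adds: "These data will be pulled from the electronic health record". Only the patient ID and the test date are needed. No matching query of test counts is described for the study period. Study-period events come from section 9.3 (Subsequent Visits): "At each consultation, either through phone or face to face visit, the clinician who contacts the patient will log on the spreadsheet". The code list there has one code for app tests (APP-6MWT) and another for the "Regular clinic 6MWT" (CLINIC-6MWT), with the example entry "Date: 23/4/2021, distance: 450m". An app test is logged only if the patient shares it and it is at most two weeks old.

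**The concern.** Clinic tests can be expected during the study. Section 7 allows consultations by phone or in clinic, section 5.4 has patients called in when the app shows deterioration, and section 9.3 provides a code for the resulting tests. Two analysts following section 12.1 could therefore report different study-period figures, one counting app tests only and the other counting all tests.

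The change of source is a separate problem, and settling the counting rule does not remove it. A drop in clinic tests between the two periods could reflect fewer tests or incomplete logging, and the plan gives no means of telling these apart.

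At stake is the interpretation of a secondary outcome. Section 17.2 says the study aims to cut the number of patients who need to visit the PH clinic. Readers will want to know whether app tests came in place of clinic tests or on top of them, and one figure of unstated composition cannot show that.

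**Working it through.** The documents state no test rate, effect size or precision for this comparison, so there is no figure to reproduce. The check sets the texts side by side and then works out when the counting rule matters.

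**Step 1: what counts during the study.**

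| Place | Study-period tests |
|---|---|
| Synopsis and section 6, objectives tables | total, no mode stated |
| Section 12.1, counting sentence | available results, no mode stated |
| Section 12.1, following sentence | app tests |
| Section 9.3, codes | app and clinic tests logged under separate codes |

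None of these says which codes enter the study-period figure.

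**Step 2: sources.** Clinic tests before the pandemic come from the health record, and clinic tests during the study from the consultation log. The three-monthly check in section 14 covers the presence and spelling of keywords and the consistency of the data. It does not describe reconciling counts with the record. Section 14.2 says there is no monitoring.

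**Step 3: effect of the counting rule.** Per patient-year, let B be clinic tests before, A app tests during and C clinic tests during.

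- App-only change: A - B
- All-test change: A + C - B
- The two differ by C, so the app-only figure understates total testing whenever C > 0.
- The sign reverses only if A < B < A + C, that is, C > B - A > 0.

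All rates below are assumed.

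| B | A | C | App only | All tests | Reversal |
|---|---|---|---|---|---|
| 2.0 | 1.5 | 0.8 | -0.5 (-25%) | +0.3 (+15%) | yes |
| 2.0 | 1.5 | 0.5 | -0.5 (-25%) | 0 | no |
| 2.0 | 1.0 | 0.5 | -1.0 (-50%) | -0.5 (-25%) | no |
| 2.0 | 3.0 | 1.0 | +1.0 (+50%) | +2.0 (+100%) | no |

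In the first row, clinic tests alone change by (0.8 - 2.0)/2.0 = -60%. Separate lines would show clinic testing down and total testing up.

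**Step 4: effect of the source.** Suppose both codes are counted but only a share p of study-period clinic tests is logged. The all-test change is then A + pC - B, which is positive only if p > (B - A)/C. With the first row's rates this is 0.5/0.8 = 62.5%. If less than that share were logged, a true rise would appear as a fall. The documents give no value for p.

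**The case against.** The strongest reply is that the plan already counts all tests. The outcome is defined as a total, and the counting sentence in section 12.1 has no mode limit. The words about the app come in a sentence of purpose rather than a counting rule. When the authors mean app tests only, as in the primary analysis, they say so. The two codes are separate, so study-period app, clinic and total counts can be tabulated from the planned log. The outcome is secondary and descriptive, with no test or threshold.

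Much of this stands. A reader might infer from the sentence about the app that clinic tests during the study have no place in the data or the analysis. The documents do not support that: CLINIC-6MWT captures them with date and distance, and the outcome definition is wide enough to include them. What is missing is a statement of the counting rule.

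On sources, it can be said that section 9.2 describes only the baseline request, that section 12.1 does not end its five years at the pandemic, and that section 14 mentions three-monthly analysis of data on the health record. None of these describes a study-period query of test counts. It is fair to add that no text calls the earlier record complete or shows that the log undercounts. The objection is that the sources differ and no reconciliation is planned, not that an undercount is known.

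**Conclusion.** The point holds as a fault in the counting rule and in the match of sources. Section 12.1 is inconsistent on which tests form the study-period figure. Under every reading, no health-record count of clinic tests is planned for the study period to match the one before the pandemic.

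An app-only figure understates total testing by exactly the study-period clinic rate. A reader might go further and infer that the direction of the result will reverse. The documents do not support that. Reversal needs an app rate below the earlier clinic rate and a study-period clinic rate above that shortfall, and no rates are given. The -25% against +15% contrast rests on assumed rates. If the app rate equals or exceeds the earlier clinic rate, or no clinic tests occur, an app-only count cannot reverse the direction. If both codes are counted, no reversal arises from the counting rule, though the source mismatch remains.

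The primary outcome is unaffected. The change is still worth making, because it is cheap and lets the comparison separate clinic testing from app testing.

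**What to change.** 1. In section 9.2 (Baseline Assessments), extend the record query for patient ID and 6MWT date to the end of the study. Clinic tests then come from one source in both periods. Use the CLINIC-6MWT rows as a cross-check and report any disagreement.
2. In section 12.1, state the counting rule and report clinic, app and total tests per patient-year on separate lines, before and during the study. Bring the sentence about the app into line with this.
3. State beside the table that the app and total rates during the study are lower bounds, because app tests are logged only if shared and recent. Extending the record query does not remove this limit.

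The cost is a later end date on a query already planned, two more lines in one table and a sentence of text. No new patient contact is needed.
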